6.4.2.2 Pharmacokinetic analysis set

All patients who have evaluable pharmacokinetic data without any protocol deviations deemed to effect the pharmacokinetics of AZD6140 will be included in the summaries and listings of the pharmacokinetic data.

6.4.2.3 Safety analysis set

All patients who received at least one dose of study medication will be included in the assessment of safety.

6.4.3 Methods of statistical analyses

Statistical analysis will be carried out by Biostatistics at AstraZeneca, Wilmington, Delaware using SAS (version 8.2). Graphics to be included in the text or intended for use as supplemental figures and individual profile figures will be made using SAS or other software. Pharmacokinetic analysis will be carried out by, or under the guidance of, the Pharmacokinetic Section, Experimental Medicine, at AstraZeneca, Wilmington, Delaware.

No formal statistical analysis of the pharmacodynamic, pharmacokinetic or safety data will be done.

6.4.3.1 Pharmacodynamic

The respiratory parameters will be descriptively summarized by treatment and listed by individual at each time point by treatment and visit using descriptive statistics. These will also be supported with graphical displays in order to ease making comparisons.

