The respiratory parameters, and changes from baseline, will be summarized at each scheduled time point by treatment and visit using descriptive statistics. These will also be supported with graphical displays in order to ease making comparisons.

The plasma concentrations and pharmacokinetic parameters of AZD6140 and AR-C124910XX will be descriptively summarized. Furthermore, graphical plots of the respiratory parameter and concentration of AZD6140 will also be explored.

Safety data (adverse events, vital signs, 12-lead ECGs, laboratory data, physical examination data) will be summarized at each scheduled time point by treatment for each of the 2 cohorts using descriptive statistics.

The results of genetic analysis will be exploratory and will not be included in the clinical study report.

TABLE	OF CONTENTS	PAGE
	TITLE PAGE	1
	PROTOCOL SYNOPSIS	3
	TABLE OF CONTENTS	7
	LIST OF ABBREVIATIONS AND DEFINITION OF TERMS	12
1.	INTRODUCTION	15
1.1	Background	15
1.2	Rationale	16
2.	STUDY OBJECTIVES	17
2.1	Primary objective	17
2.2	Secondary objective(s)	17
3.	STUDY PLAN AND PROCEDURES	17
3.1	Overall study design	17
3.1.1	Screening/Visit 1	
3.1.2	Period I/Visit 2	18
3.1.3 3.1.4	Period II/Visit 3	19
3.1.5	Follow-up/Visit 4	20
3.2	Rationale for study design, doses and control groups	25
3.3	Selection of study population	27
3.3.1	Study selection record	27
3.3.2	Inclusion criteria	27
3.3.3	Exclusion criteria	27
3.3.4	Restrictions	
3351	Criteria for discontinuation	
3.3.5.2	Procedures for discontinuation	
3.3.5.3	Procedures for Discontinuation from Genetic aspects of the study	31
3.4	Treatment(s)	32
3.4.1	Investigational Product(s)	32
3.4.1.1	Identity of investigational product	32
3.4.1.2	Labelling	33
3.4.1.3	Storage	
5.4.1.4 2.4.2	Accountability	
3.4.2 3.1.2	Method of assigning patients to treatment groups	
344	Blinding and procedures for unblinding the study	
5.1.1	2 mang and procedures for anomanig the study	

3.4.4.1	Methods for ensuring blinding	
3.4.4.2	Methods for unblinding study	
3.4.5	Concomitant medication	
3.4.6	I reatment compliance	
4.	MEASUREMENT OF STUDY VARIABLES	37
4.1	Medical examination and demographic measurements	37
4.1.1	Enrollment medical examination and demographic measurements	
4.1.2	Post-study medical examination	38
42	Pharmacokinetic measurements	38
421	AZD6140 and AR-C124910XX	38
4211	Determination of drug concentration in biological samples	38
4.2.1.2	Collection and processing of biological samples for determination of	

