2. STUDY OBJECTIVES

2.1 **Primary objective**

The primary objective of the study is to:

• Assess the effect of AZD6140 on respiratory rate and minute ventilation.

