3. STUDY PLAN AND PROCEDURES

3.1 Overall study design

This will be a randomized, double blind, 2 cohort, placebo-controlled, PK/PD, single center study to assess the effect of AZD6140 on respiratory parameters in mild asthma patients aged 35 to 75 years (inclusive) and mild to moderate COPD patients aged 55 to 75 years (inclusive). Up to 12 men or women will be randomized in each cohort to ensure at least 8 patients complete the trial within each cohort.

On Study Day 1 of Period I, each patient will receive one of the following treatments according to the randomization schedule:

Treatment A: A single, oral dose of 450 mg AZD6140 (5 x 90 mg micronised tablets) will be administered in the AM of Study Day 1; followed by a single, oral dose of 180 mg AZD6140 (2 x 90 mg micronised tablet) in the PM (12 hours after the first dose); thereafter, 180 mg AZD6140 (2 x 90 mg micronised tablet) will be administered bid (every 12 hours) on Study Days 2 and 3 and in the AM only on Study Day 4.

Treatment B: A single, oral dose of AZD6140 matching placebo (5 placebo tablets) will be administered in the AM of Study Day 1; followed by a single, oral dose of AZD6140 matching placebo (2 placebo tablets) in the PM (12 hours after the first dose); thereafter, AZD6140 matching placebo (2 placebo tablets) will be administered bid (every 12 hours) on Study Days 2 and 3 and in the AM only on Study Day 4.

At the end of Period I, all patients will crossover to receive the alternate treatment following at least a 7 outpatient day washout period. During each treatment period, pharmacodynamic measurements and safety variables will be assessed. Blood samples will be collected for analysis of AZD6140 and its metabolite, AR-C124910XX.

3.1.1 Screening/Visit 1

In order to establish eligibility to participate in the study, potential patients will undergo all screening procedures and assessments within 21 days before Day 1 of Period I, after giving written informed consent. Please refer to Table 1 and Section 4.1.1 for procedures and assessments to be completed at the screening visit.

3.1.2 Period I/Visit 2

Each day will be based on a 24-hour clock beginning at midnight (00:00).

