This will be a double-blind, randomized, 2 cohort, placebo-controlled, 2-period crossover, pharmacokinetic/pharmacodynamic study. Mild asthma and mild to moderate COPD patients are included so that qualification of the differences in physiologic response and subjective experience of dyspnea can be extrapolated to the expected treatment population. The age range encompasses that of the Phase II study where dyspnea was first observed.

The primary variable will be respiratory rate and minute ventilation, based on the hypothesis of affecting adenosine receptors and preclinical observations. Cardiopulmonary cycle exercise testing is included because provocation of the system may elicit measurable changes in physiological parameters that are not otherwise observed. A sub-maximal protocol will be used for the exercise testing, and patients may terminate the test prior to experiencing dyspnea if they experience symptoms, which limit further exercising. Exercise testing also provides an opportunity to simulate the conditions and study the respiratory responses that could contribute to the sensation of dyspnea during daily activities.

A loading dose of 450 mg is chosen to maximize the potential of eliciting dyspnea. This dose will establish safety margins for a clinical loading dose that may be up to 270 mg. Dosing to 3 days will allow for attainment of steady-state plasma concentrations. Again, this will provide for assessment of dyspnea under clinically relevant conditions. A placebo crossover will be performed because dyspnea is a highly subjective sensation, and therefore comparison to a placebo baseline is desirable. In a healthy elderly volunteer study presently completing in the clinic this dose was well tolerated with no reports of dyspnea to date. This study will conclude the clinical phase prior to the start of the respiratory study in mid asthma and mild to moderate COPD patients.

Genetic polymorphisms may affect patients' responses to drugs. Genetic analysis on genes that may be involved in development of dyspnea associated with AZD6140 treatment will improve the understanding of the potential mechanism of this effect of AZD6140. Due to the limited number of patients in this study and low incidence of dyspnea associated with AZD6140 treatment, all patients participating in the study will be required to donate blood for genetic analysis.

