3.4.2 Doses and treatment regimens

Each patient will receive each of the following treatments in one of two treatment sequences (AB or BA) according to the randomization schedule:

Treatment A: A single, oral dose of 450 mg AZD6140 (5 x 90 mg micronised tablets) will be administered in the AM of Study Day 1; followed by a single, oral dose of 180 mg AZD6140 (2 x 90 mg micronised tablet) in the PM (12 hours after the first dose); thereafter, 180 mg AZD6140 (2 x 90 mg micronised tablet) will be administered bid (every 12 hours) on Study Days 2 and 3 and in the AM only on Study Day 4.

Treatment B: A single, oral dose of AZD6140 matching placebo (5 placebo tablets) will be administered in the AM of Study Day 1; followed by a single, oral dose of AZD6140 matching placebo (2 placebo tablets) in the PM (12 hours after the first dose); thereafter, AZD6140 matching placebo (2 placebo tablets) will be administered bid (every 12 hours) on Study Days 2 and 3 and in the AM only on Study Day 4.

All doses given in each treatment will be administered with 240 mL of room temperature water while the patient is sitting in an upright or in a semi-recumbent position. Patients must remain either sitting or semi-recumbent for at least 2 hours after each dose intake.

On Study Days 1 and 4 of each treatment, the patients will receive the AM study medication following an overnight (10 hour) fast and will continue to fast for 3-4 hours post dose. On Study Day 4 of each treatment, the patients will be allowed to drink water beginning 2 hours after study drug administration and patients should be encouraged to drink water in order to maintain an adequate hydration state for the cycle exercise test.

The PM dose on Study Days 1, 2 and 3 will be given either 1 hour before or 2 hours after food intake. On Study Day 2 and 3, breakfast will be served 1 hour after the AM study medication.

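### For the primary variables, the crossover plan specifies no within-patient AZD6140-minus-placebo difference, no spread for it and no interval, and its two descriptions of the summary disagree

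*Combined protocol and SAP*

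**What the plan says.** The primary objective (Section 2.1) reads: "Assess the effect of AZD6140 on respiratory rate and minute ventilation". The design is an AB/BA crossover (Section 3.4.2): "Each patient will receive each of the following treatments in one of two treatment sequences (AB or BA) according to the randomization schedule". Section 3.2 gives the reason for the placebo period: dyspnea is subjective, "therefore comparison to a placebo baseline is desirable". On numbers, Section 3.1 says: "Up to 12 men or women will be randomized in each cohort to ensure at least 8 patients complete the trial within each cohort".

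The only pharmacodynamic variable derived is the change from baseline within each period (Section 6.1.2). The pharmacodynamic set requires evaluable respiratory data in both periods (Section 6.4.2.1). On analysis, Section 6.4.3 says: "No formal statistical analysis of the pharmacodynamic, pharmacokinetic or safety data will be done".

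The summary is described twice, differently:
- Section 6.4.3.1: "The respiratory parameters will be descriptively summarized by treatment and listed by individual at each time point by treatment and visit using descriptive statistics". Read naturally, the summary is by treatment and the individual listing is by treatment and visit.
- Synopsis, statistical methods: "The respiratory parameters, and changes from baseline, will be summarized at each scheduled time point by treatment and visit using descriptive statistics". Here the summary itself is by treatment and visit.

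Neither sentence mentions cohort. The synopsis does so for safety data, which "will be summarized at each scheduled time point by treatment for each of the 2 cohorts using descriptive statistics".

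**The concern.** A crossover lets each patient serve as his or her own control. The quantity that answers the primary objective is the difference between a patient's AZD6140 and placebo periods, and its uncertainty depends on how much that difference varies between patients. The plan excludes patients who cannot be paired and then never forms the pair. A reader of the report would see two columns of means and SDs, and could not tell from them whether a shift was consistent across patients or came from a few.

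Two further points affect the result. Visit 2 is Period I and Visit 3 is Period II (Table 2), so the choice between the two summary texts decides whether a cell mixes sequences or holds one only. And Section 2.2 sets out to compare asthma patients, COPD patients and healthy volunteers, which needs the respiratory results by cohort.

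**Working it through.** **Inputs.** From the documents: sequences AB and BA; up to 12 randomised and at least 8 completers per cohort (Section 3.1); no sequence ratio or balance rule, and withdrawals after dosing not replaced (Section 3.4.3). No SD, within-patient correlation or target effect is given, so precision below is in units of the total SD, s, with correlation ρ assumed over a range. There is no planned figure to reproduce: Section 6.4.4 says the sample size is not power-based.

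**1. What the planned means recover.** Write d for a patient's AZD6140 value minus placebo value at one time point. With complete data both treatment columns hold the same n patients, so the difference of column means equals the mean of d exactly. Its variance does not follow from the columns: Var(d) = Var(A) + Var(B) − 2Cov(A,B), and the covariance is not summarised.

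**2. Period effect.** Let π be the Period II minus Period I shift. The AZD6140 mean carries π·nBA/n and the placebo mean carries π·nAB/n, so the raw difference carries π(nBA − nAB)/n.
- 4:4 gives 0.
- 5:3 gives 2/8 = 25% of π in size.
- 6:2 gives 4/8 = 50% of π in size.

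Imbalance is not remote. Under simple randomisation, an assumption because the rule is not stated, an exact 4:4 split of 8 has probability 70/256 = 0.27.

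The period-adjusted estimate is ½(mean d in AB + mean d in BA), which removes π. Its SE is ½·SD(d)·√(1/nAB + 1/nBA), with the SD pooled within sequence and n − 2 degrees of freedom. At 5:3 the variance factor is ¼(1/5 + 1/3) = 0.133, against 1/8 = 0.125 for the unadjusted mean. The SE rises by √(0.133/0.125) = 1.03, about 3%.

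**3. The synopsis layout.** Each treatment-by-visit cell holds one sequence. Per cohort at 1:1 that is 8/2 = 4 to 12/2 = 6 patients; with cohorts pooled it is 8 to 12. Averaging the two within-visit contrasts gives ½[(A1 − B1) + (A2 − B2)] = ½[(A1 − B2) + (A2 − B1)], the same period-adjusted estimate. So here too the point estimate is recoverable but its paired SE is not.

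**4. Precision.** 95% half-widths in units of s for one cohort, n = 8, balanced, one time point; t(6) = 2.447, t(14) = 2.145. For levels, Var(d) = 2s²(1 − ρ). For changes from baseline, assume equal correlation ρ among a patient's two baselines and two post-dose values. The two changes are then uncorrelated, each with variance 2s²(1 − ρ), so Var(d) = 4s²(1 − ρ).

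| Comparison | Formula | ρ = 0.5 | 0.7 | 0.8 |
|---|---|---|---|---|
| Levels, within-patient | 2.447·√(2(1−ρ)/8) | 0.87 | 0.67 | 0.55 |
| Levels, columns read as unpaired | 2.145·√(2/8) | 1.07 | 1.07 | 1.07 |
| Levels, cells within one visit | 2.447·√(2/4) | 1.73 | 1.73 | 1.73 |
| Changes, within-patient | 2.447·√(4(1−ρ)/8) | 1.22 | 0.95 | 0.77 |
| Changes, columns read as unpaired | 2.145·√(4(1−ρ)/8) | 1.07 | 0.83 | 0.68 |
| Changes, cells within one visit | 2.447·√(4(1−ρ)/4) | 1.73 | 1.34 | 1.09 |

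For levels, pairing narrows the interval. For changes under this correlation structure it does not: the SE is unchanged and the paired interval is slightly wider through fewer degrees of freedom. Other structures would give other answers.

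**The case against.** The strongest reply has three parts. The study is openly exploratory and feasibility-sized, with no formal analysis by choice. The treatment columns contain the same patients, so the comparison with placebo is there, and individual listings and graphs let a reader look within patients. And Section 6.4.1 promises a full SAP before database lock, which could supply the contrast, the cohort split and the layout.

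Much of this stands. Exploratory intent and the absence of a power calculation are declared and are not faults, and no hypothesis test is called for. But listings allow a reader to improvise an analysis; they do not specify one. An interval is also compatible with the exploratory aim, since Section 6.4.3.3 already allows slopes with 95% confidence intervals for the secondary PK/PD relationships. A later SAP could close the gap, but nothing in the current text requires it to, and Section 6.4.3 could be read as forbidding it.

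A reader might go further and infer that the primary objective will be judged from between-patient comparisons of 4 to 6 patients per cell. The documents do not support that. Section 6.4.3.1 summarises by treatment, only the synopsis adds visit, and either set of means returns a within-patient point estimate. The 4 to 6 also requires 1:1 sequences and a cohort split, neither of which is stated for these data.

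**Conclusion.** The point holds as a gap in specification that is cheap to close. The primary objective gets no stated within-patient estimate, no SD of the difference and no interval, in a design chosen to compare each patient with placebo. The firm quantity is the period-effect leakage into the raw by-treatment difference: 25% of any period effect at 5:3 completers and 50% at 6:2. That assumes complete data and an additive period effect. The period-adjusted estimate further assumes no carryover.

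The disagreement between the synopsis and Section 6.4.3.1, and the missing cohort split, are plain from the text and rest on no assumption.

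Two larger claims that a reader might infer should not be made. One is that the planned layout inflates the SE 2.0 to 3.2 times. That holds only for raw levels compared between cells within one visit, at ρ of 0.5 to 0.8, whereas the plan also derives changes from baseline, for which pairing may gain nothing over the by-treatment means. The other is that many time points, two variables and two cohorts make a false signal almost certain (96% over 64 contrasts). That treats correlated serial measurements as independent, in a study that plans no tests.

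**What to change.** Make the synopsis and Section 6.4.3.1 agree on whether the summary is by treatment or by treatment and visit, and state that it is by cohort.

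Add to Sections 6.1.2 and 6.4.3.1: for each cohort, derive each patient's AZD6140-minus-placebo difference in respiratory rate and in minute ventilation at each scheduled time. Report n, mean and SD of the difference, and the period-adjusted estimate (the average of the two sequence means) with its 95% CI, labelled exploratory and without a hypothesis test. A model with sequence, period, treatment and patient would also serve. State whether levels or changes from that period's baseline are used, since the working shows that this alters the precision.

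Amend Section 6.4.3 so that its exclusion of formal analysis does not bar these estimates or the slopes allowed in Section 6.4.3.3. Naming one lead summary for each primary variable would help but is optional.

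The cost is wording and a little more programming, with no new data or patients. The downside is that the intervals will show openly how imprecise 8 to 12 patients per cohort are.

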6.4.3.2 Pharmacokinetic

All pharmacokinetic parameters will be descriptively summarized by treatment and listed by individual at each scheduled time point. AZD6140 and AR-C124910XX plasma concentrations will be summarized and, reported as descriptive statistics and listed by individual at each scheduled time point.

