2.2 Secondary objective(s)

The secondary objectives of the study are to:

- Assess the effect of AZD6140 on other respiratory parameters;
- Evaluate the pharmacokinetic/pharmacodynamic (PK/PD) relationship between AZD6140/AR-C124910XX concentrations and respiratory parameters in mild asthma patients and mild to moderate COPD patients;
- Compare respiratory parameters between mild asthma patients, mild to moderate COPD patients and healthy volunteers from study D5130C00028;
- Compare PK of AZD6140 and AR-C124910XX in mild asthma patients, mild to moderate COPD patients and healthy volunteers from study D5130C00028.
- Examine the safety and tolerability of AZD6140 in mild asthma patients and mild to moderate COPD patients.

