6. PHARMACOKINETIC, PHARMACODYNAMIC, SAFETY, GENETIC AND STATISTICAL METHODOLOGY

6.1 Pharmacokinetic / pharmacodynamic evaluation

6.1.1 Calculation or derivation of pharmacokinetic variables

The pharmacokinetic analyses will be performed by Clinical Pharmacokinetics, Experimental Medicine, AstraZeneca , Wilmington, DE.

Plasma concentrations of AZD6140 and its metabolite AR-C124910XX will be listed and depicted graphically as a function of time relative to Day 1 dose for the 2 cohorts. Pharmacokinetic parameters listed below will be estimated by non-compartmental analysis.

Day 1: C_{max} , t_{max} , AUC₀₋₁₂ of AZD6140 and AR-C124910XX, and metabolite to parent C_{max} and AUC ratios

Day 4: C_{max} , t_{max} , AUC_{τ}, metabolite to parent C_{max} and AUC ratios of AZD6140 and AR-C124910XX and, AZD6140 steady state CL/F.

AZD6140 and AR-C124910XX C_{max} will be estimated as the highest measured concentration and t_{max} will be the time to maximum concentration within a dosing interval on Days 1 and 4. AUC₀₋₁₂ and AUC_{τ} will be calculated using the linear trapezoidal method over the 12 hour dosing interval on Days 1 and 4, respectively. AZD6140 CL/F will be estimated as the ratio of AZD6140 dose and AUC_{τ} on Day 4. The ratio of AR-124910XX C_{max} to AZD6140 C_{max} ratio and, AR-124910XX AUC to AZD 6140 AUC ratio will be calculated on Days 1 and 4.

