6.4.4 Determination of sample size

The sample size for each cohort was chosen based on feasibility concerns, and the need to provide adequate information to support further development. The sample size was not based on any power calculations.

- 6.5 Interim analyses (not applicable)
- 6.6 Data presentation (not applicable)

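### The secondary objective of comparing drug and metabolite exposure between asthma patients, COPD patients and D5130C00028 volunteers has no matching analysis: no cohort summary, no between-group ratio and no interval is planned.

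*Combined protocol and SAP*

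**What the plan says.** Section 2.2, like the synopsis, lists this secondary objective: "Compare PK of AZD6140 and AR-C124910XX in mild asthma patients, mild to moderate COPD patients and healthy volunteers from study D5130C00028".

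The methods that bear on it are:

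- Section 6.4.3.2: "All pharmacokinetic parameters will be descriptively summarized by treatment and listed by individual at each scheduled time point". Plasma concentrations are also summarized and listed.
- Section 6.1.1: concentrations are to be "listed and depicted graphically as a function of time relative to Day 1 dose for the 2 cohorts". The only ratios defined there are metabolite to parent, within a patient.
- Section 6.4.3: "No formal statistical analysis of the pharmacodynamic, pharmacokinetic or safety data will be done".
- Section 6.4.3.3 allows, as an option, regression slopes of respiratory endpoints on AZD6140 concentration with 95% confidence intervals.
- Section 3.1: "Up to 12 men or women will be randomized in each cohort to ensure at least 8 patients complete the trial within each cohort".
- Section 6.4.4: "The sample size for each cohort was chosen based on feasibility concerns, and the need to provide adequate information to support further development". It adds: "The sample size was not based on any power calculations".
- Section 6.4.1 promises a separate, comprehensive SAP before database lock. Its text is not in the documents supplied.

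**The concern.** The objective asks for a contrast between three groups of people. The planned split for PK parameters is by treatment, and Treatment B is placebo, where no drug exposure is expected. Followed as written, section 6.4.3.2 pools or leaves unspecified the two patient cohorts, leaves out the volunteers, and produces no between-group estimate.

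This matters beyond the PK tables. Section 1.2 includes these patients to learn how sensitive people with respiratory disease are, and section 3.2 supposes that patients and healthy volunteers differ in sensitivity to dyspnea. Section 2.2 also sets a comparison of respiratory parameters with the same volunteers. If patients respond more, part of the explanation could be higher exposure. Judging that needs an exposure ratio with its uncertainty. Without one, a reader compares summaries by eye across two studies and may take a lack of visible difference as evidence of equal exposure.

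**Working it through.** **1. Objective against method.**

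| Element the objective needs | Where section 6 provides it |
|---|---|
| PK parameters by cohort | Not stated; 6.4.3.2 splits by treatment. Only concentration listings and plots are by cohort (6.1.1). In the synopsis, the two cohorts are named for the safety summaries but not for PK |
| Volunteer data from D5130C00028 | Not mentioned anywhere in section 6 |
| A between-group effect measure | None; the only ratios are metabolite to parent |
| Uncertainty of that measure | None; the only intervals are the optional ones for concentration-response slopes (6.4.3.3) |
| A criterion for similar exposure | None |

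**2. How precise would a ratio be?** The plan states no power, margin or precision, so there is no figure to reproduce. Inputs:

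- Patients per cohort: 8 completers to 12 randomized (section 3.1).
- Volunteers: number not in the documents. Sections 1.2 and 3.2 describe a healthy elderly volunteer study ("In a healthy elderly volunteer study presently completing in the clinic this dose was well tolerated with no reports of dyspnea to date") but give no size. Assumed 8, 12 or 20.
- Between-subject CV of AUC and Cmax: not in the documents. Assumed 30% to 50%, with 20% and 60% as outer cases.

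For log-normal exposure:

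- s = sqrt(ln(1 + CV²)), which gives 0.294, 0.385 and 0.472 at CV 30%, 40% and 50%.
- 90% interval = GMR ×/÷ exp[ t(0.95, n1+n2−2) · s · sqrt(1/n1 + 1/n2) ], where GMR is the geometric mean ratio.

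Worked case, 8 vs 8 at CV 40%: t(0.95, 14) = 1.761 and sqrt(1/8 + 1/8) = 0.5. The exponent is 1.761 × 0.385 × 0.5 = 0.339, and exp(0.339) = 1.40. An observed ratio of 1.0 then has a 90% interval of 0.71 to 1.40.

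The ×/÷ factor in each case:

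| Groups | CV 20% | CV 30% | CV 40% | CV 50% | CV 60% |
|---|---|---|---|---|---|
| 8 vs 8 | 1.19 | 1.30 | 1.40 | 1.52 | 1.63 |
| 8 vs 12 | 1.17 | 1.26 | 1.36 | 1.45 | 1.55 |
| 8 vs 20 | 1.15 | 1.23 | 1.32 | 1.40 | 1.49 |
| 12 vs 12 | 1.15 | 1.23 | 1.31 | 1.39 | 1.48 |

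The COPD-to-asthma contrast depends only on this study's cohort sizes and the assumed CV. The contrasts with volunteers also depend on the assumed volunteer number.

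**The case against.** Several points on the other side have weight.

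- **The study is exploratory and disclaims power.** This stands, and it rules out a complaint that a powered test is missing. It does not explain why a stated comparison has no estimate. Section 6.4.3.3 already accepts confidence intervals in the same study.
- **The plan has more than listings.** This stands. There are descriptive summaries and cohort-level concentration plots. Patient numbers also identify the cohort (section 3.4.3), so a reader could work out a COPD-to-asthma ratio from the individual listings. That recovers one contrast by hand and none against the volunteers.
- **By treatment may be template wording.** Plausible, since sections 6.4.3.1 and 6.4.3.4 use it too. It still needs correcting for PK.
- **Concentration-response is examined directly.** Section 6.4.3.3 plots respiratory endpoints against concentration, and Table 3 requires a PK sample at each spontaneous dyspnea episode. These help separate exposure from sensitivity within the patients, but they do not cover the volunteers.
- **The separate SAP may fill the gap.** It may. Nothing in section 6 requires it to, and section 6.4.3 points the other way.
- **A cross-study interval can suggest false precision.** This stands. The documents do not give the volunteer study's size, sampling times, formulation or assay, and a pooled interval does not cover differences between studies.

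A reader might also infer that the study could not tell similar exposure from a 1.4-fold difference. The documents do not support that: 1.4 appears nowhere in them. Across the six cases of 8 vs 8 and 12 vs 12 at CV 30% to 50%, four exclude 1.4 around a ratio of 1.0 (1.30, 1.23, 1.31, 1.39), one sits on the line (1.40), and one includes it (1.52). At 8 vs 8, a 90% interval excludes 1.4 when the CV is below about 40%. Nor is limited resolution caused by the missing interval; it comes from having 8 to 12 patients per cohort.

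**Conclusion.** The point holds as a mismatch between objective and analysis. The PK comparison in section 2.2 has no corresponding contrast, no summary of parameters by cohort, and no route by which D5130C00028 data enter. If a ratio were reported, its 90% interval would be about ×/÷ 1.3 to 1.5 at 8 per group and 1.23 to 1.39 at 12 per group. That rests on an assumed CV of 30% to 50%, log-normal exposure and, for the volunteer contrasts, an assumed volunteer number. This is wide enough that similar-looking summaries are not evidence of equal exposure.

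Two further inferences are not supported. The plan does not say that arithmetic means will be used or that equal exposure will be concluded; it leaves the statistics unnamed. Adding an interval would make the imprecision visible without reducing it.

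**What to change.** **Section 6.4.3.2**

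- Replace the split by treatment with a split by cohort on active treatment.
- Report geometric means and CV for Day 1 AUC(0-12) and Cmax and for Day 4 AUC(tau) and Cmax, for parent and metabolite.
- Give the COPD-to-asthma geometric mean ratio with a 90% interval from log-transformed values.
- Give each cohort's ratio to D5130C00028 with a 90% interval, labelled as a non-randomized cross-study estimate whose interval does not cover differences between the studies.

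**Section 6.4.3**

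- State that no hypothesis tests will be done, but that these estimates with intervals will be reported.
- State that absence of a difference will not be concluded from descriptive means alone.

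**Cost.** One extra table and a minor change to protocol and SAP wording; section 5.4 requires ethics committee notification or approval for a protocol amendment. No new samples, visits or patients are needed. The D5130C00028 PK data are needed, but the objective already relies on them. The small downside is that wide intervals become visible.
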